1.5 Clinical Data to Date

Indocyanine green has been used in the clinical settings since 1957. There is a wealth of data available attesting to the safety of this drug injected at its current clinically indicated dosing level. Indocyanine green has been shown to preferentially uptake in esophageal tumors as opposed to surrounding epithelial lumen after 1 minute of IV exposure [26]. Additionally, the same group reported being able to better characterize the vascularization of the tumor to further clarify the invasiveness of the cancer. Indocyanine green usage has been shown to be safe in a similar clinical setting by the Gotoh group, who used indocyanine green

CONFIDENTIAL

This material is the property of the University of Pennsylvania.

to detect and characterize bullous and emphysematous lesion of the lung in video assisted thoracoscopic surgeries (VATS) with Infrared Thoracoscopy that were not previously detectable by white light [18]. Finally, indocyanine green has been utilized in applications relating to brain tumors. In a rat glioma model, areas imaged using indocyanine green correlated to the tumor margin within 1 mm [27]. Although dosing and the timing of administration of indocyanine green were variable, tumor demarcation was made possible with the use of intraoperative NIR imaging of indocyanine green [22]. Since then, [name] group has demonstrated uptake into human lung tumors [23]. In addition, [name] group has demonstrated uptake in human gliomas, meningiomas and brain metastasis [20, 21, 25].

Previous studies conducted in full-term pregnant women demonstrated no maternal or fetal reactions to the dye. It appeared that indocyanine green clearance is a safe and sensitive test for evaluation of liver function during pregnancy [19].

Prior and ongoing studies with solid tumors at the University of Pennsylvania using indocyanine green and imaging devices have enrolled over 500 subjects to date (17, 20, 23, 25, 28-46). The data collected from these subjects have provided us with knowledge that this method of imaging can be helpful to surgeons in the operating room, including identifying inflammatory processes in lymph nodes and metastatic disease in the thoracic cavity that was not visible on CT or PET scans (17, 20, 23, 25, 28-46).

The standard of care dye, Gleolan™, is the first *and only* FDA approved optical imaging agent for use in Fluorescence-Guided Surgery. Gleolan [aminolevulinic acid hydrochloride (ALA HCl)] is an optical imaging agent indicated in patients with glioma (suspected World Health Organization Grades III or IV on preoperative imaging) as an adjunct for the visualization of malignant tissue during surgery. It is orally administered 2-4 hours prior to anesthesia. A standard surgical operating microscope adapted with a blue light emitting light source and ancillary excitation and emission filters to visualize fluorescence excitation in the wavelength of 375 to 440 nm and for observation from 620 to 710 nm will be used to view Gleolan (50, 51, 52).

In this current study, we intend to compare SOC dyes with indocyanine green to find out which dye is more accurate and precise. This may lead to patients receiving more than one (1) drug prior to surgery and visualizing the tumor with different cameras during surgery.

There are no additional risks of administering both dyes. However, due to imaging with multiple cameras, the surgical procedure may be prolonged 15 minutes. In this study, there is no anticipated risk by extending the surgical procedure.

As of January 2019, this protocol completed Part 1, observational, and began Part 2, permitting deviation from the surgical plan based on indocyanine green intraoperative imaging, of the study. A total of 327 subjects consented with 296

CONFIDENTIAL

This material is the property of the University of Pennsylvania.

subjects receiving infusion of indocyanine green and 26 non-evaluable subjects (4 subjects have been consented but not infused as of yet). The reasons for non-evaluable subjects are the following: iodine/shellfish allergy (4 subjects), surgical procedures cancelled (4 subjects), decline participation (9 subjects), scheduling conflicts (5 subjects), and clinical issues (4 subjects; i.e., pre-infusion hypertension [HTN]; no medical clearance for surgery).

Of the 296 subjects infused, 110 subjects were administered 2.5 mg/kg and 186 subjects were administered 5 mg/kg of indocyanine green. Of 296 infusions, there were 55 total adverse events (AEs) observed in 35 patients, which are presented in more detail in [Section 1.7](#) below.

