- Adverse reactions occurring in < 1% of patients in the first 6 weeks after surgery were: chills, photosensitivity reaction, solar dermatitis, hypotension, abnormal liver function test, and diarrhea.

CONFIDENTIAL

- Neurologic events related to the surgical procedure occurred in 29% of patients and included: aphasia, hemiparesis, hemianopia, headache, seizure, hemiplegia, monoparesis, hypoesthesia, and brain edema.
- Elevated liver enzymes occurred in clinical studies.

There are no anticipated risks of dosing of simultaneous dosing of Indocyanine green and 5-ALA.

Risks of the Use of NIR Imaging Systems:

The video images that we will take intraoperatively may result in the surgeon changing the operation. He/she will not change the scale of the operation to do anything that was not described to the subject during the surgical consent process beforehand. The possible risks associated with taking these images are as follows:

- There is a chance that an area without any cancer in it will glow in the video images. If that happens, the surgeon may remove healthy tissue that did not need to be removed and that would not have been removed in a standard surgery.
- There is a chance that while removing additional tissue that glows in the video images, the subject could be put at an increased risk of having a surgical complication. A surgical complication includes, but is not limited to bleeding, infection, pain, injury to a major organ, nerve damage, blood clot in the arms/legs/other region of the body, and/or death.
- There is a chance that being under anesthesia for the extra 15-20 minutes that it takes to obtain the images for this study could put the subject at an increased risk of having of a common side effect associated with anesthesia. These common side effects include, but are not limited to nausea and vomiting after surgery, sore throat and hoarseness, shivering/chills, confusion, increased BP, and/or muscle aches.
- Finally, there is a chance that the imaging technique could falsely reassure the surgeon that all of the cancer has been taken out, so not as much tissue will be removed. In other words, not all of the cancer could be taken out.

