1.7.2 Known Potential Benefits

The purpose of this study is not to investigate a possible benefit for each subject. We do not know whether these video images truly identify cancerous tissue, so we cannot guarantee any benefits from being part of this study. However, there is a chance that because of the video images, the surgeon will remove additional cancerous tissue that they would not have removed during a standard operation.

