3.1 General Design

This study is a single center, open-label, two-part study to assess image guided surgery of intramolecular imaging in nervous system tumors. Subjects with a diagnosis of a resectable nervous system tumor who are at risk of recurrence are included. The primary goal is to observe what tissues fluoresce in the OR, and then to identify if that tissue is cancerous/tumor or normal when the histopathology is performed.

This study is split into two parts. The purpose of Part 1 is to confirm dose, assess timing of the operation and assess the feasibility of using indocyanine green as a fluorescent for neurosurgical tumor resection without extending surgery beyond what is seen on the standard of care MRI. The purpose of Part 2 is expansion of the margin view phase of the operation, where residual fluorescence can be resected at the discretion of the surgeon; in addition, further evaluation of optimal dosing and timing.

CONFIDENTIAL

Candidates are those with a presumed tumor in the nervous system that requires surgery. There is no randomization or control group.

Subjects undergo indocyanine green injection within 72 hours prior to surgery. Permitting infusion time within 72 hours of operation is believed to be adequate for tissue glow/surgical visualization. Alternately, patients may receive 25 mg of indocyanine green during induction. Dose and time of administration will be determined by the neurosurgeon during surgical planning. This 25 mg dose of indocyanine green is similar to dosing for other intraoperative vascular visualization.

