Margin View: After completion of the surgery based on standard techniques, the NIR imaging system (i.e. VS₃ Iridium, Stryker 1588 AIM) will be used to determine if there is any residual fluorescence in the resection bed. In Part 1 of this study, the surgeon will proceed to biopsy suspected areas of residual or abnormal tissue or abnormal fluorescence without extending surgery beyond what is seen on the standard of care MRI. In Part 2 of this study, the surgeon will proceed to resect suspected areas of residual or abnormal tissue or abnormal fluorescence. These biopsy and/or resected sites will be correlated with the final pathology, which will be considered the gold standard. Fluorescence of the biopsy and/or resected specimen with the NIR imaging system will be studied both *in vivo* and *ex vivo*. In addition, surgeon's judgment as to whether the biopsy and/or additional resection specimen represents tumor will be recorded in a binary outcome questionnaire (yes/no).

Final View: Last, prior to closing a final view of the cavity will be obtained with the NIR imaging system – Final View.

Ex Vivo View: Specimens will be placed in a specimen cup. These specimens will be imaged on a back table with the NIR imaging system.

Once the tumor is resected, a small section of the path specimen will be divided and appropriately labelled: 1) histopathology, 2) research lab specimen. Each tissue sample will be placed in its own unique specimen cup. The tissue will be sent to pathology for standard processing, following OSHA and Institutional policy and procedures for tissue handling and transport.

Of note, it is not always possible to be sure of diagnosis prior to surgical sampling and pathologic analysis. Nevertheless, all subjects and specimens will contribute to the final analysis. For example, if the subject is thought to harbor a malignant

CONFIDENTIAL

This material is the property of the University of Pennsylvania.

glioma, but at the time of surgery, an intraoperative diagnosis of lymphoma is made, this subject's pathology and indocyanine green fluorescence status will still contribute to the final analysis plan.

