7.1 Primary Endpoint

The primary endpoint is the sensitivity, specificity, positive predictive value, negative predictive value of indocyanine green fluorescence as compared to the gold standard – H&E histopathology.

We compute estimates of the sensitivity (fraction of path-positive margins that are called correctly) and specificity (fraction of path-negative margins that are called correctly), and calculate Bayesian 90% probability intervals around them. We estimate the sensitivity of our method by evaluating the fraction of marginal biopsy and/or resected specimens that we call correctly, and similarly estimate the specificity by the fraction of path-negative biopsy and/or resected specimens that we call correctly.

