7.2 Secondary Endpoints

For the secondary endpoint, we will use descriptive data on signal to background noise and safety data by tumor type to identify optimal dosing and timing of indocyanine green for intraoperative imaging in nervous system tumors. We will conduct an interim analysis after approximately 185 subjects are treated at the 2.5mg dose and 185 at the 5mg/kg dose.

Other important endpoints include safety and toxicity that includes review of vital signs and any reported or observed AE.

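### PPV is a primary endpoint without a formula or interval, Part 1 biopsies are pooled with Part 2 resections, and the yield of fluorescence-led resection is not tabulated

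*Combined protocol and SAP*

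**What the plan says.** Section 6.3 sets a different action at the margin view in each part. For Part 1: "In Part 1 of this study, the surgeon will proceed to biopsy suspected areas of residual or abnormal tissue or abnormal fluorescence", with the limit that surgery does not go past what the standard-of-care MRI shows. For Part 2: "In Part 2 of this study, the surgeon will proceed to resect suspected areas of residual or abnormal tissue or abnormal fluorescence". Section 3.1 makes this optional: "residual fluorescence can be resected at the discretion of the surgeon". In both parts each specimen is imaged for fluorescence in vivo and ex vivo and compared with final pathology, and the surgeon records a yes/no judgement on whether it is tumour.

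Section 1.5 gives the trial's status at a January 2019 cut-off: "this protocol completed Part 1, observational, and began Part 2, permitting deviation from the surgical plan based on indocyanine green intraoperative imaging". From this trial, 1.5 and 1.7.1 give enrolment, dose groups and adverse events. On diagnostic value, 1.7.2 says "We do not know whether these video images truly identify cancerous tissue". On the harm from a false positive, 1.7.1 says "If that happens, the surgeon may remove healthy tissue that did not need to be removed".

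Sections 3.2 and 7.1 name sensitivity, specificity, PPV and NPV against histopathology as the primary endpoint. The computing paragraph of 7.1 then defines sensitivity and specificity over biopsy and resected specimens together, "and calculate Bayesian 90% probability intervals around them". Section 7.2 bases the choice of dose and timing on signal-to-background and safety data, and adds: "We will conduct an interim analysis after approximately 185 subjects are treated at the 2.5mg dose and 185 at the 5mg/kg dose".

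**The concern.** PPV is the probability that sampled glowing tissue is tumour. In Part 2 both the hoped-for gain (more tumour removed) and the specific harm (healthy nervous tissue removed) depend on it. The plan leaves it the least specified of the accuracy measures, and three things follow.

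First, a pooled PPV mixes two sampling rules. Part 1 specimens lie within the MRI-visible extent, and Part 2 specimens need not. Predictive values move with the proportion of tumour among the tissue sampled, so the pooled figure may describe neither part.

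Second, nothing in the plan produces a PPV before the final analysis. A Part 1 estimate should be obtainable from data already held.

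Third, no endpoint isolates what the extra resection yielded. Other monitoring may not fill this gap. Section 8.4 closes the adverse-event reporting period at the end of surgery, and Tables 2a and 2b schedule no adverse-event collection afterwards. A deficit that appears later would depend on the general instruction in 8.1 that subjects report subsequent events. Section 7.3 says the study is to inform a randomised trial, and the yield per patient is an input that such a trial would need.

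**Working it through.** **Stated figure.** The only planned number is 500 subjects. Section 7.3 says there is no sample size calculation, so there is nothing to reproduce.

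**Text check of 7.1.** Four measures are named. Two have a definition (sensitivity, specificity). The interval clause follows those two and refers back to them. PPV and NPV have neither definition nor interval, and no prior is stated for any interval. Specimens from both parts enter one calculation. Section 7.4 adds only general descriptive methods.

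**Timing of the interim.** By January 2019, 186 subjects had received 5 mg/kg and 110 had received 2.5 mg/kg (1.5). Reading the lower dose in 7.2 as 2.5 mg/kg, the trigger needs 185 − 110 = 75 more subjects at that dose, so it falls no earlier than 296 + 75 = 371 infused. Even then, PPV is not among its contents.

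**Subjects still to come.** 500 − 327 consented = 173. The share infused among those with a known outcome is 296/(296 + 26) = 0.919, and 173 × 0.919 ≈ 159. (The counts 296 + 26 + 4 sum to 326, one short of 327, which makes no difference here.) The interim would therefore come after at least 75/159 ≈ 47% of them.

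**Tumour-free specimens among them (assumed inputs).** The number is subjects × specimens per subject × (1 − PPV).

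| Assumed PPV | One fluorescence-led specimen per subject | One in half of subjects |
|---|---|---|
| 0.9 | 159 × 0.1 ≈ 16 | 8 |
| 0.7 | 159 × 0.3 ≈ 48 | 24 |
| 0.5 | 159 × 0.5 ≈ 80 | 40 |

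**Precision of a PPV by the plan's own type of interval.** With x tumour-positive among n glowing specimens and a uniform prior, the limits are the 5th and 95th percentiles of Beta(x + 1, n − x + 1). The counts are assumed. The Part 1 share of the 296 infused is not given, so 296 is an upper bound at one specimen per subject.

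| x/n | 90% interval |
|---|---|
| 35/50 | 0.58 to 0.79 |
| 70/100 | 0.62 to 0.77 |
| 207/296 | 0.65 to 0.74 |

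Over the counts and PPVs examined (n from 30 to 296, PPV 0.5 to 0.9), a Jeffreys prior moves the limits by at most about 0.015.

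**Several specimens per subject.** The design effect is 1 + (m − 1) × ICC. Assuming m = 2 with ICC 0.2 gives 1.2, and m = 3 with ICC 0.5 gives 2.0. Interval width grows by √1.2 ≈ 1.10 to √2.0 ≈ 1.41. At a design effect of 2, 100 specimens carry the information of 50, which is the first row of the table.

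**Why pooling matters.** PPV = Se × p / [Se × p + (1 − Sp) × (1 − p)], where p is the proportion of tumour among the tissue sampled. With assumed Se = 0.9 and Sp = 0.7, p = 0.7 gives 0.88 and p = 0.3 gives 0.56. Equal numbers of glowing specimens from each would pool to (0.88 + 0.56)/2 = 0.72, which describes neither setting.

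**The case against.** The strongest reply is that PPV is already a named primary endpoint, that biopsies belong to the analysed specimens, and that 6.3 says all subjects and specimens contribute to the final analysis. A reader might infer that the plan never analyses Part 1 biopsies for how often glowing tissue is tumour. The documents do not support that. What is missing is a formula, an interval and a separation by part.

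A reader might also infer that no accuracy estimate existed when Part 2 opened. That cannot be shown. Section 1.5 cites publications on uptake in gliomas, meningiomas and brain metastases whose contents are not visible here, and the sentence in 1.7.2 explains why no benefit is promised to subjects. The documents show only that the protocol itself prints no Part 1 PPV.

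Two further readings also go too far. One is that the extra tissue goes unrecorded: 6.3 collects fluorescence, pathology and surgeon judgement for each specimen, and only the tabulation is absent. The other is that the safety committee sees nothing but adverse events and deaths. Section 8.5 deals with event reporting, and the monitoring plan and case report forms are attachments not available for this review.

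It is also fair to say that Part 1 was meant for dose, timing and feasibility (3.1), that resection in Part 2 is discretionary and weighed against risk (1.7.1, 3.1), that a Part 1 PPV may not carry over to tissue outside the MRI extent, and that the analyses are descriptive (7.4). These points lower the severity. The last but one is itself a reason to report by part.

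**Conclusion.** The point holds in this form and should be fixed, but it does not invalidate the trial. As written, 7.1 leaves two of its four primary measures without a definition or interval and pools specimens taken under two different rules. The interim omits accuracy, and no endpoint isolates the tissue removed because it glowed.

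The size cannot be fixed from the documents, which give neither specimen counts nor a split of the 296 infused subjects by part. The 16, 48 or 80 tumour-free specimens follow from about 159 further subjects, one fluorescence-led specimen each, and assumed PPVs of 0.9, 0.7 and 0.5. The tabulated interval widths rest on assumed counts and independent specimens, and clustering would widen them.

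Even when fully specified, PPV will describe only the fluorescent tissue that surgeons chose to sample, since glowing tissue left in place has no pathology.

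**What to change.** (a) In 7.1, define PPV (path-positive among fluorescent specimens) and NPV (path-negative among non-fluorescent specimens). Report them with sensitivity and specificity separately for Part 1 and Part 2. Give all four 90% Bayesian intervals, with the prior stated and a method that allows for several specimens per subject.

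(b) Run the Part 1 PPV analysis on the data already held and add PPV to the interim in 7.2. Give both results to the DSMC, with a note that Part 1 sampling was limited to the MRI extent.

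(c) In 7.2, define fluorescence-led extra tissue from the fields in 6.3. For Part 2, tabulate the proportions of subjects with any such tissue, with at least one path-positive extra specimen, and with only path-negative extra tissue, each with an interval. If the case report form does not record why a specimen was taken, one added field would be needed.

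What follows from these figures is for the sponsor and the DSMC to decide.

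The cost is a few sentences of plan text and one more descriptive look at accuracy. The result may also be a less favourable risk statement in 1.7.

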1.6 Dose Rationale

In this study, the indocyanine green dose began at 5 mg/kg, aligned with previous nonclinical and clinical experience at the University of Pennsylvania. Given the incidence of HTN in our CNS cohort and seeking optimal signal to background ratio, we decreased to 2.5 mg/kg to assess efficacy and safety. Thus, we intend to evaluate dose ranges but will not exceed 5mg/kg. Alternately, based on neurosurgeon plan, patients may receive a 25 mg bolus of ICG at the time of induction administered intravenously by the anesthesiologist. This 25 mg dose of indocyanine green is similar to dosing for other intraoperative vascular visualization. This can cause less usage of the drug, lower risk of adverse event occurrences.

We make no changes to the route of administration.. The most important difference between what is labeled on the package and this protocol is the dose regimen (up to 5 mg/kg) and the amount of time elapsing before intraoperative imaging begins (up to 72 hours). This protocol began with 24-hour infusions the day before surgery based on previous nonclinical and clinical experience at the University of Pennsylvania. Interested in strength of signal to background ratio over extended or shortened timeframes, we allow for a range of up to 72 hours. The rationale for dosing timing prior to surgical intervention is based on the minimal risks with indocyanine exposure, to accommodate logistical scheduling of surgeries, and to collect data on optimal signal to background ratio in various tumor types.

Indocyanine green has been used in a dose-escalation trial up to a maximum dose of 10 mg/kg [\[22\]](#) and in other trials 3-5 mg/kg [\[13, 17-21\]](#). Indocyanine green has a LD₅₀ after IV administration of 50 to 75 mg/kg [\[22\]](#).

As [name] and other researchers have used an IV injection of indocyanine green to obtain imaging sufficient to describe discrepancies in the structure of abnormal hyper-vascularized tissue [\[47\]](#), it therefore stands to reason that we would be able to accomplish our objective of imaging tumors with indocyanine green using a similar dose.

CONFIDENTIAL

This material is the property of the University of Pennsylvania.

Interim data analysis (see [Section 7.2](#)), specifically the fluorescence signal to background ratio, will determine the optimal timing of indocyanine green infusion, which will guide future infusion in this protocol and future protocols.

